3.4.3 The cerebral vaso-reactivity to arterial carbon dioxide

The cerebrovascular reactivity to changes in arterial carbon dioxide tension is tested in mechanically ventilated newborns.

Inclusion criteria:

- gestational age <37 weeks
- postnatal age at least 24 hours
- mechanically ventilation
- clinical stability
- normal brain ultrasound
- transcutaneous pCO2 monitoring (tcpCO2)

In case of hypercapnia (tcpCO2>7 kPa) or hypocania (tcpCO2<5 kPa) clinical changes in ventilatory settings are introduced according to routine clinical care in order to normalise pCO2. At least 20 min is allowed to assess the full effect of the change in ventilator setting. This may be repeated if necessary to normalise the tcpCO2.

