3.5. Data recording and management

Subjects are sequentially numbered. The list of subjects with their basic clinical data will be recorded in an electronic file.

During all measurements, NIRS data will be stored timelocked with other monitored

variables as relevant (arterial oxygen saturation, transcutaneous pCO2, mean arterial blood pressure, pulse rate).

Before analysis all data will be graphed and screening for artefacts by visual inspection. After removal of artefacts, the data will be locked.

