3.6.2 Data analysis

- (4.1) The SpO2, StO2, oxygen extraction (OE: SpO2-StO2), fractional oxygen extraction (FTOE: SpO2-StO2)/SpO2), CBFi, and cerebral metabolic rate of oxygen index (CMRO2i: OE x CBFi) will be graphed versus time after cord clamping. It is expected that StO2 will rise by about 30%, and that CMRO2i and FTOE will remain relatively constant. The results will be compared to the literature.
- (3.4.2) Reproducibility (test-retest variability) will be determined by ANOVA.
- (3.4.3) Data containing 0.5 kPa change in tcpCO2 or more within 15 minutes after a change in ventilator settings will be analyses for CBFi-tcpCO2 reactivity. One minute of data just before the change and one minute of data 15 minutes later will be used. The expected reactivity is 30%/kPa.
- (3.4.4) Signal loss will be calculated per 24 hours. This will be compared to the results of the SafeBoosC-II. The system operations and sensor manipulations will be classified into suitable groups and tabulated. The mean Likerts scores will be calculated and the free text comments classified and typical comments used *verbatim* in the reporting process.

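### CO2 reactivity is read from two single minutes although more data are recorded: a modest loss of precision whose size depends on assumptions

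*Protocol*

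**What the plan says.** Protocol section 3.6.2 selects episodes for the CO2 sub-study by a minimum tcpCO2 change ("Data containing 0.5 kPa change in tcpCO2 or more within 15 minutes after a change in ventilator settings") and then fixes the readings: "One minute of data just before the change and one minute of data 15 minutes later will be used". It adds a benchmark: "The expected reactivity is 30%/kPa".

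Two other sections show that more data will exist than this rule uses. Section 3.5 states: "During all measurements, NIRS data will be stored timelocked with other monitored" variables, among which it lists tcpCO2. Section 3.4.3 states: "At least 20 min is allowed to assess the full effect of the change in ventilator setting". It also allows further steps in the same infant: "This may be repeated if necessary to normalise the tcpCO2".

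On artefacts, section 3.5 describes visual screening and then: "After removal of artefacts, the data will be locked". The protocol does not say what happens when an artefact falls in one of the two chosen minutes. Section 3.6.1 assigns 20 infants to this sub-study, without a precision target.

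**The concern.** The reactivity is a before-after difference in CBFi divided by the change in tcpCO2. Spontaneous fluctuation in either reading goes straight into the numerator. At the smallest qualifying change, 0.5 kPa, the expected signal is 30 × 0.5 = 15% of CBFi, and dividing by 0.5 doubles any noise. A longer average on each side would usually reduce that noise using data already stored. With a read-out at 15 minutes and at least 20 minutes allowed, about five minutes are available on the after side.

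At stake is the width of the interval that will be set against 30%/kPa in a group of only 20 infants. A second, weaker worry is that an artefact in a required minute could cost the episode.

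**Working it through.** The protocol gives no precision calculation for this sub-study, so there is no figure of its own to reproduce.

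**Inputs from the protocol:** one minute on each side, read-out at 15 minutes, minimum change 0.5 kPa, expected reactivity 30%/kPa (all 3.6.2); at least 20 minutes after a change (3.4.3); 20 infants (3.6.1).

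**Assumptions, because the protocol gives no figures:** noise SD c = 10% of CBFi per one-minute mean; correlation ρ^k between minutes k apart (AR(1)); between-infant SD τ = 10%/kPa; one step per infant; noise in tcpCO2 ignored.

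**Step 1: noise variance of the difference, in units of c².** The comparison is minute −1 against minute 15 (16 minutes apart), or minutes −5 to −1 against minutes 15 to 19.

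- One-minute windows: V1 = 2(1 − ρ^16).
- Five-minute windows: V5 = 2A − 2B. A = [5 + 2(4ρ + 3ρ² + 2ρ³ + ρ⁴)]/25 is the variance of one window mean. B is the average of ρ^lag over the 25 pairs of minutes, with lags 16 to 24.

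Example at ρ = 0.5: A = [5 + 2(2 + 0.75 + 0.25 + 0.0625)]/25 = 0.445 and B is negligible, so V5 = 0.890 against V1 = 2.000. The noise SD ratio is √(0.890/2.000) = 0.667.

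**Step 2: standard error of the mean reactivity for a change of Δ kPa.** SE = √[(τ² + c²V/Δ²)/20].

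At ρ = 0.5:
- Δ = 1: √[(100 + 200)/20] = 3.87 against √[(100 + 89)/20] = 3.07.
- Δ = 0.5: √[(100 + 800)/20] = 6.71 against √[(100 + 356)/20] = 4.77.

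| ρ | V1 | V5 | noise SD ratio | SE at 1 kPa, 1 min → 5 min | fall | SE at 0.5 kPa, 1 min → 5 min | fall |
|---|---|---|---|---|---|---|---|
| 0.5 | 2.000 | 0.890 | 0.667 | 3.87 → 3.07 | 21% | 6.71 → 4.77 | 29% |
| 0.8 | 1.944 | 1.423 | 0.856 | 3.84 → 3.48 | 9% | 6.62 → 5.79 | 13% |
| 0.9 | 1.629 | 1.455 | 0.945 | 3.63 → 3.50 | 3% | 6.13 → 5.84 | 5% |
| 0.95 | 1.120 | 1.125 | 1.002 | 3.26 → 3.26 | none | 5.23 → 5.24 | none |

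The fall in the SE is smaller than the fall in noise SD, because between-infant variation is untouched by the windows. At ρ = 0.95 the wider windows also lie further apart on average (20 minutes instead of 16), which cancels the benefit.

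**Step 3: is the one-minute estimate still usable?** With t = 2.093 on 19 degrees of freedom, the largest one-minute SE in the table gives these 95% half-widths:
- 1 kPa: 2.093 × 3.87 = 8.1, or 30 ± 8%/kPa.
- 0.5 kPa: 2.093 × 6.71 = 14.0, or 30 ± 14%/kPa.

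Both intervals are clear of zero.

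**Step 4: artefacts.** If each minute is unusable with probability p, independently, and any affected minute is void, the share of episodes lost is 1 − (1 − p)². For p = 5%, 10% and 20% this is 9.75%, 19% and 36%, or about 2, 4 and 7 of 20. The protocol supplies neither p, nor independence, nor the voiding rule.

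**The case against.** The case for leaving the rule alone is substantial.

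- **Same answer.** A prespecified minute on each side is clear and computable. A reader might infer that two single minutes make the comparison with 30%/kPa uninformative; step 3 shows that they do not under these assumptions. This stands.
- **Smallest gain where it is most wanted.** If the noise is slow spontaneous drift in flow, ρ is high and the benefit shrinks to 3 to 5% or nothing. This stands.
- **Artefacts.** A reader might infer that one artefact loses the episode. The protocol does not say so. A partly cleaned minute may keep usable data, artefacts may cluster, and a repeated step can give the infant another episode. A substitution rule may also sit in an analysis plan that is not at hand. This stands, so the percentages in step 4 are conditional only.
- **The wider window has costs.** CO2 and flow may still be moving between 15 and 20 minutes, since section 3.4.3 allows at least 20 for the full effect. If a step is repeated at 20 minutes, the after window of one step could double as the before window of the next. Nothing guarantees five recorded minutes before a change made in routine care. These points limit the remedy and must be built into its wording.
- **Not the only check on flow.** This is the only sub-study with an induced change, but CBFi is also examined after birth under section 3.6.2. A reading that the device's flow signal rests on this test alone goes too far.

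What does not stand is that the matter is simply left to a later plan. The protocol itself names the two minutes, and a plan that follows it inherits them.

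**Conclusion.** The concern holds as a minor precision weakness. The protocol fixes a two-minute estimator while timelocked data over a longer period are stored. For autocorrelation from 0.5 to 0.9, five-minute windows would lower the SE of the mean by 21% to 3% at a 1 kPa step and by 29% to 5% at 0.5 kPa. These figures rest on the assumed 10% minute noise, 10%/kPa between-infant SD, AR(1) correlation and 20 infants with one step each. Loss of episodes remains a possibility without a size.

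The difference between the 15-minute read-out in section 3.6.2 and the period of at least 20 minutes in section 3.4.3 is a separate matter. Those passages must be reconciled, and the point about window width applies wherever the read-out is placed.

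**What to change.** Replace the one-minute rule in section 3.6.2 with a matched-window rule:

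- The before value is the mean of the artefact-free CBFi data in up to five minutes before the ventilator change.
- The after value is the mean of the artefact-free CBFi data in up to five minutes from the planned read-out, and this window ends before any further ventilator change.
- tcpCO2 is averaged over exactly the same minutes as CBFi.
- No minute belongs both to the after window of one step and to the before window of the next.
- The one-minute estimate is kept as a sensitivity analysis.

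Saying up to five minutes covers episodes with a shorter recording before the change, and a later read-out if the timing passages are reconciled that way.

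The cost is wording only, with no extra measurement. The downside is a slight blur if tcpCO2 or CBFi is still drifting within a window. Averaging both over the same minutes limits this, and the sensitivity analysis would show a material effect. The protocol is a draft due to become a clinical investigation plan, so the change can be made then.

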3.7. Safety

The BabyLux system is used non-invasively and, therefore, carries no significant risk for the patients involved. It is worth mentioning that DCS and TRS, like NIRS, are totally safe since they employ nonionizing radiation with typically a very low power. It has been estimated that the light intensity on the brain surface during NIRS can be safely estimated to be only a few per cent of the solar irradiation [Kiguchi M, 2007]. Moreover, both DCS and TRS based instruments have been tested for safety by the appropriate offices in several institutions. In particular a DCS based instrument is a non-significant risk (NSR) device as defined by Food and Drug Administration (FDA) and therefore does not require FDA approval for investigational use. The DCS based instrument has been approved for laser safety in both USA and Europe. TRS based instruments have been recently approved for studies on neonates by the Italian Ministry of Health [Document DGDFSC.VI/P//I 5 i m 2/2012/874, Ministero della Salute, 27/03/2013]. Similarly, the safety and feasibility of TRS measurements on neonates and preterm babies have been extensively demonstrated in the United Kingdom within the framework of the nEUROPt project (Noninvasive imaging of brain function and disease by pulsed near infrared light, EU FP7 Cooperation STREP - HEALTH-2008-201076).

Classification PU

The BabyLux system is a medical device not bearing CE marking and intended for clinical investigation. According to the existing procedures at national and European level, the BabyLux medical device will request the authorisation from the Italian Ministry of Health to conduct clinical investigation according to this clinical protocol.

Rare reversible local skin reactions, such as rashes and burns, have been observed underneath NIRS sensors in very preterm babies. These adverse events can be further minimised by frequently moving the placement the sensor.

Pulse oximetry and transcutaneous pCO2 monitoring are non-invasive technologies that are universally used and accepted for standard care of newborn infants.

3.8. Ethical considerations

The approval from the relevant ethics committees will be sought. Parental informed consent will be obtained. The measurements will be conducted in compliance with the guidelines of the Declaration of Helsinki in its latest form and the International Conference on Harmonisation good clinical practice guidelines (ICH GCP). Procedures will be established to prevent and/or minimise risk of complication for participants.

3.9. Financial issues

All financial issues will be covered by the BabyLux project (EUROPEAN COMMISSION, ICT Policy Support Programme, Competitiveness and Innovation Framework Programme, Grant agreement no: 620996).

3.10. Personal data

Child's personal medical data collected as part of the trial will be processed in accordance with the data protection legislation of the European Medicines Act. Independent persons or representatives of the regulatory authorities (e.g., regional council, federal superior authority and ethical committees) appointed to monitor clinical studies may have access to child's medical files.

Parental information sheets, consent forms will be added before submission for ethical approval late spring 2014. An investigator brochure will be developed in collaboration with the technical partners and the protocol will be modified into a clinical investigation plan as required for approval by the national authorities (device agencies) of Italy and Denmark.
